7.3 ASSESSMENT OF PARTICIPANT COMPLIANCE WITH STUDY INVESTIGATIONAL PRODUCT

Compliance for this study includes making both stimulation sessions. Participants have the ability to schedule their second stimulation 1-3 weeks after the first. Follow-up emails will be sent out 2 days after scheduled visit.

8 POTENTIAL RISKS AND BENEFITS

8.1 BENEFITS TO SUBJECTS AND SOCIETY

Chronic pain is a debilitating disorder that involves problem in the feedback (top-down) mechanism in pain processing. Our novel approach introduces non-invasive brain stimulation for brain dysfunction and has the potential to treat symptoms not only in chronic pain, but also in depression and schizophrenia ([name], 2015; [name] et al., 2016). Additionally, tACS has the potential to provide a treatment option that is safe, scientifically-supported, low-cost, easy-to-administer method to effectively reduce symptoms in patients suffering from chronic pain. The chance to understand and develop a new treatment for chronic pain is an important step in helping the millions of people in the world who suffer from its effects, from physical handicaps to common psychiatric comorbidities including opioid addictions and depression. If tACS is feasible and effective for patients with chronic pain, findings will provide persuasive preliminary results for the National Institutes of Health (NIH) and National Institute of Mental Health (NIMH) proposals to fund a large-scale clinical trial for patients with this serious disorder.

This study has not been designed to benefit the individual participants. However, participants in this study may experience some degree of relief from chronic pain symptoms as a result of tACS treatment. There are no serious risks to the participant from the treatment used in this study.

8.2 POTENTIAL RISKS

8.2.1 PSYCHOLOGICAL

Risk of Embarrassment: Self-report and clinical assessments contain questions regarding sensitive personal information. This risk is necessary in order to assess symptomology. Participants will be assured upon intake that only study personnel will see any clinical ratings.

Risk of Confidentiality. All subjects will be informed during the consent process that if they report violent or suicidal ideation/behavior, this information will be kept confidential unless the subject reports a plan to hurt themselves or an identified victim. In this case, appropriate referrals will be made and the subject will be advised to end their participation in the study.

In the unlikely event of a breach of confidentiality, people might discover that an individual was involved in this research study. Some people might not agree with the principle of participating in research or of changing natural brain activity. To avoid breaches in confidentiality, study documents that contain personal information, including the informed consent, and the document that links study ID numbers to personal identifying information are kept in locked filing cabinets in locked rooms, separate from any source documents containing participating dummy identifiers. All data is stored in locked cabinets inside locked offices; electronic data will be stored only on password-protected computers, and data encryption methods will be used during communication between investigators. Only study personnel will have access to these data. All study staff participate in annual human participating training that includes education about responsibilities to minimize the risk of confidentiality breach.

8.3 REFERRALS FOR MEDICAL FOLLOW-UP OR PSYCHOLOGICAL COUNSELING

There is a purely theoretical likelihood that stimulation of neuronal circuits can lead to epileptic discharge. To minimize this occurrence, we screen and exclude patients with personal and family history of neurological conditions from the study. If abnormalities or a seizure is witnessed during the course of the study, a referral will be made to the UNC Department of Neurology for follow-up. In the theoretical event that a seizure is witnessed that involves the loss of consciousness, the patient will be told not to operate a motor vehicle until cleared by the DMV.

We will be using the Hamilton Psychiatric Rating Scale for **Depression** (HAM-D) to assess depression and suicide risk at the initial session. Inclusion criteria states that the patient must be low suicide risk, potential participants that have an above “low risk” designation that is currently clinically relevant will not be eligible for the study.

To ensure participant comfort, a study coordinator or research assistant will periodically check in with the participant about any side-effects he/she may be experiencing during each stimulation session. Following the conclusion of the stimulation session, the participant will receive an Adverse Effects Questionnaire to report on any of the side-effects he/she may have experienced. This questionnaire reports side-effects on a likert scale (1=Absent, 2=Mild, 3=Moderate, 4=Severe). If the participant reports side-effects of Moderate to Severe intensity, a study coordinator or research assistant will discuss the side-effects experienced and note this response. The medical monitor will be contacted based on the reported intensity on the Adverse Events Questionnaire and the participant’s verbal confirmation of intensity.

8.3.1 PREGNANCY FOLLOW-UP

Every female participant will take a pregnancy test on Day 1 of Stimulation. If, after testing negative at Day 1 of Stimulation (meeting inclusion criteria), a participant reports becoming

pregnant during the course of the study, she will be withdrawn from further participation. There are no plans to follow participants who become pregnant while enrolled in the study.

Periodically, the study coordinator should also choose one CRF/eCRF and Source Document to assess for completion and maintenance. In addition, the PI will assess completeness of data on REDCap. The PI has read-only access. This allows the PI to view reports that provide information on any missing data on an individual participant basis, but does not allow the PI to add, change, or input any data.

A data safety monitor will review blinded AEs every month. The DSMB will assess recruitment and will only evaluate safety if an unanticipated concern arises.

9.3 EARLY WITHDRAWAL OF PARTICIPANTS

9.3.1 REASONS FOR WITHDRAWAL

A study participant will be discontinued from further participation if:

- The participant meets any exclusion criteria (either newly developed or not previously recognized).
- Anything that, in the opinion of the investigator, would place the participant at increased risk or preclude the participant's full compliance with or completion of the study.

Participants are free to withdraw from participation in the study at any time upon request.

9.3.2 DATA COLLECTION AND FOLLOW-UP FOR WITHDRAWN PARTICIPANTS

We will collect safety data on any participant discontinued because of an AE or SAE. In any case, every effort will be made to undertake protocol-specific follow-up procedures. If voluntary withdrawal occurs, the participant will be asked to continue scheduled evaluations and complete an end-of-study evaluation. If an AE has been reported, researchers will help the participant seek the medical care they need and a follow-up will be performed by the PI and Co-I. In the case of an early withdrawal, the researcher will make a note to file indicating this.

9.4 TERMINATION OF STUDY

If a seizure occurs at the time of a study visit, a temporary hold will be placed over the study and further investigation will ensue. This could lead to stopping the study prematurely or continuing on with further safety measures in place. If two seizures are witnessed during the study visits, the entire study will be stopped prematurely. These individuals would be referred for further medical attention. It is very unlikely that a seizure will occur, given that previous studies using tDCS in patients with depression and schizophrenia have had no seizures occur (Berlim et al., 2013).

The study will also be stopped (at least temporarily) if studies provide evidence that transcranial current stimulation caused brain damage or other harmful effects on subjects, either short-term or long-term. Examples of findings that might trigger a safety review are the number of SAEs overall, the number of occurrences of a particular type of SAE, severe AEs/reactions, or increased frequency of events.

The reasons for stopping the study and asking for further investigation include:

- Increased pain due to treatment (>25% of participants asked to seek additional health care)
- If a seizure occurs during a study visit, a temporary hold will be placed on the clinical trial

The IRB will also be informed promptly and provided the reason(s) for the termination of suspension of by the investigator, as specified by the applicable regulatory requirement(s).

10 SAFETY & REPORTING

It is important to assess safety over the course of this study. This section describes in detail how safety is assessed, reporting of Adverse Events, Serious Adverse Events, and Unanticipated Problems. This section is a reference for internal use.

10.1 SAFETY PARAMETERS

SUICIDE RISK. Participants with high suicide risk (SI or SB) will be excluded from our study.

STIMULATION SIDE EFFECTS. A stimulation adverse effects questionnaire used in previous studies will be administered at the end of each stimulation session and at the 4 week follow-up visit. This questionnaire will be used as a safety measure and to collect data on participant experience. The adverse effects questionnaire asks participants to respond on a 4 point likert scale on the severity of symptoms experienced during the stimulation session (1 = absent, 2 = mild, 3 = moderate, 4 = severe). The side effects listed are headache, neck pain, scalp pain, tingling, itching, ringing/buzzing noise, burning sensation, local redness, sleepiness, trouble concentrating, improved mood, worsening of mood, dizziness, flickering lights, and other (specify). Participants are also asked to rate on a 5 point likert scale how related they believe the side effects to be to stimulation (1 = no relation, 2 = remote, 3 = possible, 4 = probable, 5 = definite).

In addition to this survey, the study coordinator or research assistant will periodically check in with the participant during the stimulation session to assess side effects.

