4 BASIC STUDY DESIGN

This study is a pilot clinical trial with a randomized, double-blind, crossover design. This is a single site study with 2 arms. We estimate six months to complete study enrollment.

Figure 1.

Active sham treatment will include 10 seconds of ramp-in to 1 minute of 10 Hz tACS with a ramp-out of 10 seconds for a total of 80 seconds of stimulation. The choice of an active sham is motivated to enhance success of patient blinding by mimicking skin sensations associated with tACS. 10 Hz tACS will have a 10 second ramp-in and ramp-out with 40 minutes of stimulation for a total of 2420 seconds of stimulation. Stimulation waveform is a sine-wave with peak-to-peak amplitude of 2 mA. In both arms, participants will stay in a relaxed yet controlled state by watching a nature movie (“Reefscape”) during stimulation.

Eligible participants who complete this clinical trial will have a total of 2 visits; 2 days of stimulation (with 1-3 weeks in between). Day one of stimulation will take approximately 2.5 hours as eligibility will be confirmed at the beginning. Day 2 of stimulation will take approximately 2 hours. Two days after each stimulation day, participants will receive via email a follow-up survey to complete that will take approximately 15 minutes. We estimate that total participation will be approximately 6 hours over the course of 6 weeks. All time estimates take into consideration breaks and time variance in administration.

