5.2.2 DAYS 2 OF STIMULATION (VISIT 2)

Prior to starting any study procedures, female participants will be asked to take a urine pregnancy test to ensure continued eligibility. The ODI, DVPRS, 5xSST, FTF, and pressure pain threshold test will be administered before stimulation. A resting state EEG will be recorded for 5 min before and after stimulation. The participant will receive 40 minutes of sham or 10 Hz tACS stimulation (as per the initial randomization) while watching “Reefscape”. The stimulation will be followed by the pressure pain threshold, 5xSST, FTF, stimulation adverse effects questionnaire and perceived improvement ending the session.

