5.3 FOLLOW-UP

5.3.1 FOLLOW-UP EMAIL

Two days after both sessions of stimulation, participants will receive an email with a follow up survey to assess any change in pain perception. The ODI and DVPRS will take approximately 15 minutes to complete.

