6.4 SAFETY MEASURES

We will be monitoring the safety of our participants throughout the study with the following measures. These measures are listed below and can be found in the attached documents.

- A. A stimulation adverse effects questionnaire used in previous studies (IRB #14-1622, #14-3285, and #14-0600) will be administered at the end of each stimulation session. This questionnaire will be used as a safety measure and to collect data on participant experience. Please see *10.1 Safety Parameters* for more information.
- B. More as needed. Refer to previous IRB applications as needed.

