7.2 PREPARATION AND ADMINISTRATION OF STUDY INVESTIGATIONAL PRODUCT

After participants have completed the daily questionnaire, they will be comfortably seated. The researcher(s) will first measure their head using the 10-20 system for accurate electrode placement. Participants will then be fitted with the 3 electrodes for stimulation. Electrodes will be applied using Ten20 conductive paste, 5x5cm electrodes placed over F3 and F4 with a 5x7cm placed over CZ as a return electrode. The participant will be in a relaxed yet experimentally controlled state by watching "Reefscape". One session of stimulation will be performed per day for 40 minutes. For the 10 Hz tACS stimulation, there will be a 10 second ramp-in and ramp-out with 40 minutes of stimulation for a total of 2420 seconds. Stimulation waveforms are sine-waves with a peak-to-peak amplitude of 2 mA. The sham stimulation will include 10 seconds of ramp-in to 1 minute of 10 Hz tACS with a ramp-out of 10 seconds for a total of 80 seconds of stimulation. As a covariate, heart rate will be recorded throughout stimulation.

Stimulation devices will be programmed and codes will be randomized to one of the two experimental arms. Researchers will enter the participant-specific code into the App that controls the stimulation and monitor participants during the 40 minutes of stimulation.

The study coordinator and/or the research assistant will be thoroughly trained and have trainings documented on the transcranial stimulation device and will be present during all stimulation sessions. To monitor side effects of stimulation, a daily questionnaire will be administered after each stimulation session.

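### Section 10.1 relies on a four-week visit that the schedule lacks; separately, no contact after a session is shown to ask about new side effects beyond pain, disability, pain impact and possibly mood

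*Combined protocol and SAP*

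**What the plan says.** **The visit.** Section 10.1 states that the adverse effects questionnaire "will be administered at the end of each stimulation session and at the 4 week follow-up visit". Section 4 says that participants who complete the trial "will have a total of 2 visits; 2 days of stimulation (with 1-3 weeks in between". Section 6.4 places the same questionnaire at one time only: it "will be administered at the end of each stimulation session". Section 7.3 mentions only emails two days after a visit. The last column of Appendix A is the email two days after the second stimulation.

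**What later contacts ask.** Under 5.3.1, two days after each session "participants will receive an email with a follow up survey to assess any change in pain perception", and "The ODI and DVPRS will take approximately 15 minutes to complete". At visit 2, section 5.2.2 says that "female participants will be asked to take a urine pregnancy test to ensure continued eligibility" and then that "The ODI, DVPRS, 5xSST, FTF, and pressure pain threshold test will be administered before stimulation". Appendix A marks the HAM-D at both visits without placing it before or after stimulation. It marks review of medical history and of concomitant medications at phone screening and first stimulation only. Section 3.3.2 adds a reminder call or email for day 2.

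**The form and the record.** Section 7.2 says: "To monitor side effects of stimulation, a daily questionnaire will be administered after each stimulation session". The same section has participants complete a daily questionnaire before they are seated for electrode placement, without describing its content. Section 10.1 words the adverse effects form around symptoms felt in the session. Section 10.2.1 undertakes to document every adverse event in the trial, whether or not it is related to tACS.

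**The concern.** Two separate matters.

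First, staff following 10.1 would have to hold a visit that is described nowhere else, or leave out a safety assessment that 10.1 requires.

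Second, the undertaking in 10.2.1 is broad, but the scheduled questions after a session are narrow. The monthly blinded adverse event review in 9.1 uses this record, and 9.4 gives a rising frequency of events as one example of what might prompt a safety review. Section 9.3.1 also discontinues anyone who newly meets an exclusion criterion, which is only useful if staff learn of it before the second 40-minute stimulation. Effects that outlast the session are not foreign to the plan: 2.3 relies on tACS having sustained effects on alpha oscillations.

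**Working it through.** The plan states no figure to reproduce here. The check is a calendar and a side-by-side reading.

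**Calendar.** Inputs: session gap of 1 to 3 weeks (Section 4), emails 2 days after each session (5.3.1, 7.3). Take session 1 as day 0.

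- Session 2: day 7 to day 21.
- Last scheduled contact (second email): 7 + 2 = day 9 to 21 + 2 = day 23.
- Four weeks from session 1: day 28, which is 28 − 23 = 5 to 28 − 9 = 19 days after the last contact.
- Four weeks from session 2: 7 + 28 = day 35 to 21 + 28 = day 49, which is 28 − 2 = 26 days after the last contact.

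On either count the visit falls after every scheduled contact, so it cannot be one of the emails under another name.

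Section 4 also gives about 6 weeks of participation (day 42). That exceeds the 23-day maximum and lies inside days 35 to 49, but the protocol does not say how the 6 weeks was derived.

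**Contacts after a stimulation, other than that session's own end-of-session form.**

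| Contact | Source | What it is shown to ask |
|---|---|---|
| Email 1 | 5.3.1 | ODI, DVPRS |
| Day 2 reminder | 3.3.2 | Nothing stated beyond the reminder |
| Visit 2 before stimulation | 5.2.2 | Pregnancy test, ODI, DVPRS, 5xSST, FTF, pressure pain threshold |
| Email 2 | 5.3.1 | ODI, DVPRS |

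Section 6.1 describes the DVPRS as a pain rating with supplementary questions on how pain affects daily living. The HAM-D at visit 2 may touch on mood. None of the four contacts is shown to ask an open question about new symptoms.

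**The session-end form.** Section 10.1 lists 14 named items plus a free-text other, 15 in all. Because the form asks about symptoms during the session, the free-text line at visit 2 does not reach back over the preceding 7 to 21 days. Insomnia, which 10.2.1 uses as an example of a mild adverse event, is not among the 14. Whether the pain scales or HAM-D would pick it up cannot be told, because their items are not in the document.

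**Size of the remedy.** One question at three existing contacts (email 1, visit 2 before stimulation, email 2) for 20 participants: 3 × 20 = 60 answers at most.

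**The case against.** The four-week phrase looks like a slip. Several sections and the telephone script agree on two sessions, and section 10 introduces itself as an internal reference. That stands: deleting the phrase is close to clerical.

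On the second matter, the strongest reply is that it argues from absence in lists known to be incomplete. Section 5.2.2 omits the HAM-D that Appendix A marks at visit 2, the daily questionnaire of 7.2 and the EKG of 6.3.2. Section 5.3.1 names the ODI and DVPRS without saying the emails hold nothing else, and Appendix A does not itemise the emails. The instruments are in attachments not provided here. Section 12.5 says adverse events and concomitant medications are entered in REDCap, though not when they are asked about. All of this stands, so the claim is limited to what the documents show. The daily questionnaire may cover part of the gap at visit 2; it would not cover the period after session 2.

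It is also fair that the expected effects in 8.2.2 (tingling, burning or itching under the electrodes, and headache) are all on the session-end form, that staff are easy to reach (3.3.2), that known events are followed up within a week (10.4), and that insomnia comes from a generic severity scale rather than a list of tACS effects. These points reduce the consequence. They do not supply a scheduled question.

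A reader might infer that a seizure between sessions would go unnoticed. The documents do not support that: 8.3 treats the risk as purely theoretical, and a participant could well report one unprompted.

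**Conclusion.** Both parts hold, and together they are a cheap improvement rather than a threat to the trial. The four-week visit in 10.1 is current text that conflicts with Sections 4, 5.3, 6.4, 7.3 and Appendix A. Separately, at none of the four later contacts is a question shown about new side effects beyond pain, disability, the impact of pain on daily living and possibly mood. The record promised in 10.2.1 would therefore depend mainly on volunteered reports for later effects. This assumes that the attached emails and the daily questionnaire contain no such question; the document does not show either way.

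Four stronger readings should be resisted:

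- **Missed events.** The 20 × 2 = 40 post-session periods without a documented question are not a count of missed events; the number missed cannot be derived.
- **Treatment comparison.** Each participant receives both conditions under the same collection, so no bias between active and sham is evident. No effect on the HRV or pain outcomes is claimed.
- **The 9.4 pain trigger.** Pain is asked about after each session, so this criterion is not called into question.
- **Origin of the phrase.** The 6 weeks in Section 4 would fit a visit four weeks after session 2, but that does not show one was planned. Nor do the documents show that the phrase was carried over from another protocol.

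**What to change.** 1. Delete the reference to the four-week visit from 10.1. If the visit is intended, add it to Section 4, 5.3 and Appendix A, say which session the four weeks run from, and reword the form to cover the period since that session. Restoring the visit with the present wording would not capture later effects. Check at the same time what the 6 weeks in Section 4 was based on.
2. Add one open question to both existing two-day emails, for example: *Have you had any new or worse symptom since your session? What was it, when did it start, and is it still present?*
3. Add to 5.2.2 and Appendix A one question on new events, diagnoses or medicines before the second stimulation, or state that the daily questionnaire in 7.2 already asks this. Section 9.3.1 can then be applied before current is given. The same question would let staff check the week without certain over-the-counter medicines that 3.1 requires before stimulation sessions.

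Cost: text edits in 10.1, 5.2.2, 5.3.1 and Appendix A, at most 60 short answers, a few minutes of participant time, and some extra minor adverse events to log. No extra visit is needed if the four-week visit is removed.
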